### **Treatment plan:**

All procedures will be done under completely aseptic conditions.

Patients will be anaesthetized by buccal and palatal infiltration.

Crestal incision and full thickness mucoperiosteal flap will be elevated buccally and lingually. Then the bone width will be measured again using bone caliper to confirm the implant width as detected in CBCT.

Sequential drilling will be started by the pilot drill till the last drill that suited the planned implant size. Before implant placement a parallel pin will be used to check the implant parallelism.

Implant insertion will be done in the osteotomy site using torque wrench by self-tapping fashion till the implant will be placed 0.5-1mm below the alveolar bone crest with adequate primary stability

The site will be prepared to receive the graft and allow its fixation.

### **Randomization**

The study will be used simple randomization to allocate patients into test and control groups.

Then, random allocation will be performed using computer-generated random numbers to determine which group they will be assigned

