## **Patients and methods**

### **Patient selection**

This investigation will be included 12 implants placed in 12 patients with missing maxillary tooth in the esthetic zone. Subjects will be selected from the outpatient clinic, Department of oral Medicine and Periodontology, Faculty of Dentistry, Minia University.

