### **Ethical regulation**

The complete treatment plan will be explained to all patients including detailed steps, risks, and expected results and their full signed consent will be obtained prior to entry into study. The study will be complied with the rules

set by the International Conference on Harmonization Good Clinical Practice Guidelines, and the Declaration of Helsinki and the research ethics committee of the Faculty of Dentistry, Minia University.

Clinical evaluation:

Patients will be evaluated clinically and radiographically along the course of the study at baseline, 6, 12 months after the implant insertion.

The following records will be performed:

1-Clinical photographs, Study casts at baseline.

2-A preoperative cone beam computed tomography (CBCT) will be performed for each patient prior to the surgery to determine bone height and width and decide the implant length and diameter to be placed and to evaluate the underlying bone condition.

3-Full mouth periodontal parameters will be recorded using William% graduated periodontal probe to evaluate the periodontal status (plaque index, gingival index, pocket depth, clinical attachment loss).

4-Trans-gingival probing will be done at the mesial line angle 2, 4 and 6 mm apical to the gingival margin. At the same apico-coronal direction three points will be recorded at the mid-buccal and at the distal line angle (**Rotenberg & Tatakis, 2014**).

5-The width of keratinized gingiva will be measured using graduated periodontal probe and recorded as the distance from the mucogingival junction to the gingival margin

Assessment methods:

Patients will be evaluated clinically and radiographically along the course of the study (immediate after the implant insertion) at baseline 0, 6 and 12 months.

Clinical assessment:

Clinical parameters will be included: gingival thickness (GT), keratinized tissue width (KTW)

GT will be measured by trans gingival-piercing of the tissues using an anesthetic needle with a rubber stopper 2mm coronal to the MGJ and in the mid distance mesio-distally. KTW will be measured at the mid buccal area from the gingival crest to the MGJ

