Soft Tissue Augmentation by Xenogeneic Collagen Matrix Versus Subepithelial Connective Tissue Gra

Statistical Analysis Plan

Document Type: Statistical Analysis Plan

NCT Number: (To be assigned)

Document Date: July 3, 2021

Submitted by:

[name]

PhD Candidate

Faculty of Dentistry

Minia University

1. Study Identification

- Protocol ID: 505/2021
- Sponsor: Minia University
- Investigator: [name] [name] Candidate

2. Study Objectives

- To compare the clinical outcomes of xenogeneic collagen matrix (XCM) and subepithelial connective

3. Endpoints

- Primary Endpoint: Change in peri-implant soft tissue thickness at 12 months (in mm).

4. Study Design Summary

- Randomized controlled trial with two parallel arms.
- 20 patients (10 per group), assigned to either SCTG or XCM group.
- Outcome assessed by a blinded evaluator.

5. Sample Size Justification

- Based on clinical experience and prior literature, a sample size of 10 per group was determined to

6. Statistical Methods

- Descriptive statistics (mean, SD) will be used for baseline characteristics.
- Independent Samples T-test will be used to compare changes in soft tissue thickness between groups.
- Significance level set at $p < 0.05$.
- Confidence interval: 95%

7. Missing Data Handling

- Missing values will be managed using pairwise deletion. No imputation methods are planned.

8. Software to be Used

- Statistical analysis will be conducted using SPSS version 25 (IBM Corp.).

9. Data Presentation

- Data will be presented in tables (means \pm SD).
- Results will be illustrated using bar charts to compare primary outcomes.

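### Simple randomisation does not secure the SAP's 10 per group: 20 patients split 10:10 in only 17.6% of trials and 7:13 or worse in 26.3%, at a modest average cost in precision

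*Protocol*

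**What the plan says.** The Protocol's Randomization section has two sentences. The first names the method: "The study will be used simple randomization to allocate patients into test and control groups". The second gives the source of the sequence: "random allocation will be performed using computer-generated random numbers to determine which group they will be assigned". Neither mentions blocks, a cap on arm size, stratification or a list with equal numbers of each treatment.

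The SAP's section 4 describes a "Randomized controlled trial with two parallel arms" and fixes the arm sizes: "20 patients (10 per group), assigned to either SCTG or XCM group". Its section 5 again rests on 10 per group. The SAP does not name a randomisation method.

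The Protocol's own total is different: "This investigation will be included 12 implants placed in 12 patients with missing maxillary tooth in the esthetic zone". It gives no number per arm.

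**The concern.** Simple randomisation means that each patient's allocation is independent of the others, so the final arm sizes are left to chance. The SAP states those sizes as fixed. Neither document says how an equal split would be reached.

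Two things are at stake. One is precision: in a trial of 12 or 20 patients, a lopsided split noticeably widens the confidence interval for the primary comparison. The other is reproducibility: if the trial reports exactly 10:10, a reader cannot tell whether a restricted list, chance or later adjustment produced it.

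The validity of the t-test is not in question.

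**Working it through.** **Inputs.**
- Method: simple, unrestricted (Protocol, Randomization).
- Total: 20, as 10 + 10 (SAP section 4), or 12 (Protocol, Patient selection).
- Primary analysis: independent-samples t-test on change in thickness, at the 0.05 level (SAP section 6).
- Assumed: allocation probability 0.5, implied by two arms of 10 but not stated; a two-sided test; and a power anchor, because the available text gives no effect size or SD.

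The SAP's 10 per group cannot be reproduced for that last reason, and the section 5 sentence is cut off in the copy reviewed, which is not counted against the plan. For orientation, 10 per arm gives 80% power at two-sided 0.05 for a standardised difference of 1.325; 6 per arm needs 1.796.

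**Step 1: distribution of arm sizes.** P(k in one arm) = C(N,k)/2^N. The tails below count both directions.

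N = 20, 2^20 = 1,048,576:
- 10:10: 184,756/1,048,576 = 17.6%
- 7:13 or worse: 2 × 137,980/1,048,576 = 26.3%, so 8:12 or better is 73.7%
- 6:14 or worse: 2 × 60,460/1,048,576 = 11.5%

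N = 12, 2^12 = 4,096:
- 6:6: 924/4,096 = 22.6%
- 4:8 or worse: 2 × 794/4,096 = 38.8%
- 3:9 or worse: 2 × 299/4,096 = 14.6%

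**Step 2: precision.** The variance of a difference in means is proportional to 1/n1 + 1/n2. Relative to equal arms, 7:13 gives (1/7 + 1/13)/(2/10) = 1.099, a standard error 4.8% larger. At N = 12, 3:9 gives (1/3 + 1/9)/(2/6) = 1.333, a standard error 15.5% larger. Averaged over the binomial splits with both arms non-empty, the variance ratio is 1.060 at N = 20 and 1.116 at N = 12.

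**Step 3: power.** This uses the noncentral t with N − 2 degrees of freedom and noncentrality d/√(1/n1 + 1/n2), with d set so that equal arms give 80%.

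| N | Equal | Moderate split | Poor split | Worse split | Average over all splits |
|---|---|---|---|---|---|
| 20 | 80.0% | 8:12, 78.4% | 7:13, 76.2% | 6:14, 72.9% | 77.8% |
| 12 | 80.0% | 5:7, 78.9% | 4:8, 75.3% | 3:9, 68.1% | 76.0% |

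If equal arms are anchored at 70% instead, the averages are 67.7% (N = 20) and 65.9% (N = 12). At 90% they are 88.3% and 86.7%. The average loss is therefore about 2 points at N = 20 and 3 to 4 points at N = 12, whichever anchor is used.

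**Step 4: what the remedy gives up.** With a shuffled list of n + n labels, anyone counting knows the rest once one arm is full. The chance that at least the last m allocations are known is 2·C(2n−m, n)/C(2n, n). Summed over m, this averages 1.82 allocations for n = 10 and 1.71 for n = 6. The chance of three or more is 21.1% and 18.2%.

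**The case against.** Simple randomisation is legitimate and leaves no allocation deducible from earlier ones. The SAP's 10 per group can be read as a target. The average cost is small: losing one patient from each arm (9:9) raises the standard error by √(10/9) − 1 = 5.4%, more than the 4.8% from a 7:13 split. The conflict over the total matters far more. With perfectly equal arms, 12 patients give about 54% power at the difference for which 20 give 80%. The operator must know each treatment, so a fixed list lets anyone keeping count work out the last few allocations. Equality at allocation also does not guarantee equality at analysis, because the SAP leaves missing values unimputed.

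Much of this stands. The point is one of efficiency and of agreement between documents, and it ranks below settling the total. The power figures are illustrations. No document states 6:6, so the figures for 12 patients show risk and contradict no stated arm size.

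The objection does not remove the mismatch: as written, the method misses the SAP's arm sizes in about 82% of trials of 20. Nor does the average describe the tail. At 12 patients, about one trial in seven would have three or fewer patients in one arm, and a 3:9 split costs about 12 power points on the 80% anchor.

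**Conclusion.** The concern holds. The Protocol's written method does not deliver the arm sizes that the SAP states. The split percentages are exact and need only a 1:1 allocation probability. The power losses also need a two-sided test and an assumed anchor, but change little as the anchor moves from 70% to 90%.

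This should be changed, although it does not threaten validity. The argument rests on the tail risk and the near-zero price of removing it. Most chance imbalance in baseline thickness comes from the small total and would remain with equal arms.

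**What to change.** First settle whether the total is 12 or 20. Then replace the simple-randomisation sentence in the Protocol's Randomization section with wording such as:

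*Patients will be allocated 1:1 from a computer-generated random permutation of equal numbers of SCTG and XCM labels (10 + 10 or 6 + 6, according to the final total). The list will be prepared before enrolment and concealed until each patient's eligibility is confirmed.*

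Permuted blocks of randomly varying size that sum to the total would also serve. If an equal shuffled list was already intended, naming it is enough. Repeat the method in SAP section 4 so that the documents agree.

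The cost is one sentence and a different computer list, with no extra patients, visits or analyses. The drawback is the end-of-list predictability shown above, which concealment does not remove for anyone who keeps count.

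Any further rule linking disclosure of the allocation to the baseline measurement should wait until the Protocol's definition of baseline is reconciled; its assessment-methods text places baseline after implant insertion.

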#### **Group1 (control group):**

SCTG will be from the palate by single incision technique .The SCTG will be placed in the pouch over the recipient site below the labial/buccal flap and extending palatally. The graft will be sutured in a horizontal mattress manner to the labial/buccal flap .The palatal wound from which the SCTG harvested, will be sutured by sterilized, natural non absorbable silk

#### **Group2 (test group):**

The matrix was shaped to match the desired size in the recipient bed.

**Radiographic assessment:**

-Radiographic evaluation will be performed for all patients at baseline, 6 and 12 months following treatment by using cone beam CT

**Post-Operative Care:**

post operatively Antibiotic cover will be prescribed in the form of Amoxicillin-clavulanate potassium (Augmentin) 2x1000mg/day and ketoprofen 150 mg twice per day for 5 days after implant insertion. All patients were asked to perform the following measures after each surgical time: Cold packs for the first 3 hours, Soft diet for the first week, warm chlorhexidine gluconate 0.1% mouth wash twice per day in the second post-operative day and was continued for two weeks. Avoid touching of the surgical site while brushing and eating. The sutures were removed after 7 - 10 days post-surgically, one week later the operation site was again checked to ensure complete soft tissue healing. Implants loading will be done 4 months after placement and final prosthesis be delivered.

**Statistical analysis:**

-All data will be tabulated and analyzed by statistical method

Soft Tissue Augmentation by Xenogeneic Collagen Matrix Versus Subepithelial Connective Tissue Gra

Statistical Analysis Plan

Document Type: Statistical Analysis Plan

NCT Number: (To be assigned)

Document Date: July 3, 2021

Submitted by:

[name]

PhD Candidate

Faculty of Dentistry

Minia University

1. Study Identification

- Protocol ID: 505/2021
- Sponsor: Minia University
- Investigator: [name] [name] Candidate

2. Study Objectives

- To compare the clinical outcomes of xenogeneic collagen matrix (XCM) and subepithelial connective

3. Endpoints

- Primary Endpoint: Change in peri-implant soft tissue thickness at 12 months (in mm).

4. Study Design Summary

- Randomized controlled trial with two parallel arms.
- 20 patients (10 per group), assigned to either SCTG or XCM group.
- Outcome assessed by a blinded evaluator.

5. Sample Size Justification

- Based on clinical experience and prior literature, a sample size of 10 per group was determined to

6. Statistical Methods

- Descriptive statistics (mean, SD) will be used for baseline characteristics.
- Independent Samples T-test will be used to compare changes in soft tissue thickness between groups.
- Significance level set at $p < 0.05$.
- Confidence interval: 95%

7. Missing Data Handling

- Missing values will be managed using pairwise deletion. No imputation methods are planned.

8. Software to be Used

- Statistical analysis will be conducted using SPSS version 25 (IBM Corp.).

9. Data Presentation

- Data will be presented in tables (means \pm SD).
- Results will be illustrated using bar charts to compare primary outcomes.

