#### **Inclusion criteria:**

- 1-Selected patients of both sexes are 25-55 years old.
- 2-Patient will be free from any systemic diseases that might affect healing, or complicate the surgical procedures according to modified Cornell Medical Index(**Glick M.,2003**)
- 3- Thin tissue biotype ,Trans-gingival periodontal examination will be made 2, 4 and 6 mm apical to the gingival margin at the mesiolabial and distolabial line angle as well as midlabial (**Cuny-Houchmand et al., 2013**)
- 4- Cooperative, motivated, and hygiene conscious patients.

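### Cheap improvement, not an error: state that baseline thickness is the pre-graft reading, then prespecify ANCOVA on it in place of the unadjusted t-test on change

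*SAP*

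**What the plan says.** The primary endpoint in SAP section 3 is "Primary Endpoint: Change in peri-implant soft tissue thickness at 12 months (in mm"). The time from which change is measured is not given. SAP section 6 states that "Independent Samples T-test will be used to compare changes in soft tissue thickness between groups", at the 0.05 level with a 95% confidence interval, and names no covariate. SAP section 4 has "20 patients (10 per group), assigned to either SCTG or XCM group"; the protocol (Patient selection) has 12 patients.

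On allocation, the protocol (Randomization) says "The study will be used simple randomization to allocate patients into test and control groups". No stratification on thickness is mentioned.

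On baseline, the protocol's assessment methods (under Ethical regulation) give the timing as "immediate after the implant insertion) at baseline 0, 6 and 12 months". The Treatment plan places graft-site preparation directly after implant insertion: "The site will be prepared to receive the graft and allow its fixation".

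On the measurement, "GT will be measured by trans gingival-piercing of the tissues using an anesthetic needle with a rubber stopper 2mm coronal to the MGJ", midway mesio-distally. Entry requires "Thin tissue biotype ,Trans-gingival periodontal examination will be made 2, 4 and 6 mm apical to the gingival margin", which refers to different points.

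**The concern.** There are two linked matters.

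**Adjustment.** A change score subtracts baseline with a fixed coefficient of 1. If the regression slope of 12-month on baseline thickness is not 1, part of any chance baseline difference stays in the treatment estimate. Such differences are common with 12 or 20 patients and no balancing. ANCOVA estimates the slope instead. Fixing the model in advance also prevents an adjustment chosen only after an imbalance has been seen.

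**Which baseline.** Implant and graft appear to belong to one operation. A reading just after insertion could precede or follow the graft. A post-graft reading is itself affected by treatment. Change from it would describe shrinkage or remodelling, not gain from grafting, and the planned t-test would be affected as much as ANCOVA.

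**Working it through.** **Inputs.** From the documents: the test, the 0.05 level (two-sided assumed), 10 per arm (SAP section 4), or 6 per arm if the protocol's 12 patients hold and split equally. The documents give no SD at baseline (SD0), no SD at 12 months (SD12) and no correlation r. The readable text of SAP section 5 contains no effect size, SD or power, so there is no planned figure to reproduce. Assumed: r = 0.3, 0.5, 0.7 and k = SD12/SD0 = 1, 1.5, 2. SAP thickness is taken to be the protocol's GT.

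**1. What the change score leaves behind.** Let D be the chance baseline difference between arms, δ the true effect and slope b = r × k. Given D, the change estimate has expectation δ + bD − D = δ − (1 − b)D. Over all randomizations D averages zero, so the estimate is unbiased, and simulated type I error is 5.0% for both tests. At 10 per arm one SE of D is √(2/10) = 0.447 SD0. With k = 1 and r = 0.5, a one-SE imbalance shifts the estimate by 0.5 × 0.447 = 0.22 SD0. Imbalance above one SE occurs in 32% of trials. In those trials, at 10 per arm and r = 0.3, 0.5, 0.7, the t-test rejects a true null in 10.2, 8.8, 7.2% (k = 1) or 7.0, 5.6, 5.0% (k = 1.5). ANCOVA stays at 5.0 to 5.1%.

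**2. Variance ratio, ANCOVA to change.** With N patients in total:

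ratio = [(N − 3)/(N − 4)] × k²(1 − r²) / [k²(1 − r²) + (1 − rk)²]

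The leading factor, the cost of estimating the slope, is 17/16 = 1.0625 at N = 20 and 9/8 = 1.125 at N = 12. Example (k = 1, r = 0.5, N = 20): 1.0625 × 0.75/(0.75 + 0.25) = 0.80.

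Power is for a difference of 1 baseline SD, change → ANCOVA, from 200,000 simulated bivariate normal trials per cell with equal arms (k = 1 and 1.5 only).

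| k | r | slope | ratio, 10/arm | power %, 10/arm | ratio, 6/arm | power %, 6/arm |
|---|---|---|---|---|---|---|
| 1 | 0.3 | 0.30 | 0.69 | 43.3 → 57.6 | 0.73 | 26.4 → 34.1 |
| 1 | 0.5 | 0.50 | 0.80 | 56.1 → 65.7 | 0.84 | 34.8 → 40.0 |
| 1 | 0.7 | 0.70 | 0.90 | 77.9 → 81.6 | 0.96 | 52.5 → 54.0 |
| 1.5 | 0.3 | 0.45 | 0.93 | 28.1 → 30.0 | 0.98 | 17.4 → 17.7 |
| 1.5 | 0.5 | 0.75 | 1.02 | 36.2 → 35.4 | 1.08 | 22.0 → 20.7 |
| 1.5 | 0.7 | 1.05 | 1.06 | 50.5 → 48.2 | 1.12 | 30.9 → 28.1 |
| 2 | 0.3 | 0.60 | 1.02 | – | 1.08 | – |
| 2 | 0.5 | 1.00 | 1.06 | – | 1.13 | – |
| 2 | 0.7 | 1.40 | 0.99 | – | 1.04 | – |

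**3. Where ANCOVA loses.** Setting the ratio to 1 gives (1 − b)² = (factor − 1)(k² − b²), which has two roots. ANCOVA loses only between them:
- k = 1: 0.88 to 1 (10 per arm), 0.78 to 1 (6 per arm).
- k = 1.5: 0.66 to 1.22, and 0.50 to 1.28.
- k = 2: 0.52 to 1.37, and 0.30 to 1.48.

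**4. Post-graft baseline.** Suppose pre-graft and 12-month means are equal between arms, but the two materials differ by d in thickness on the day. The change score then estimates 0 − d = −d, and ANCOVA on that reading estimates −b × d. For an assumed d of 0.2 to 1.0 mm the change score shows a false difference of 0.2 to 1.0 mm; ANCOVA shows 0.1 to 0.5 mm at slope 0.5.

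**5. Can the preoperative probing serve instead?** It is taken 2, 4 and 6 mm apical to the margin; GT is 2 mm coronal to the mucogingival junction. At mid-buccal the two coincide only if keratinized width is exactly 2 + 2 = 4, 4 + 2 = 6 or 6 + 2 = 8 mm. It does not clearly supply a matching baseline.

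**The case against.** The strongest case against is that nothing here is broken. The t-test is valid, and no statement in either document requires adjustment. Imbalance above one SE in 32% of trials is just a normal tail area, true of any baseline variable in any randomized trial. The large gains need equal SDs, which the documents do not support: thin-biotype entry plausibly narrows SD0, and at k = 1.5 to 2 the gain nearly vanishes or reverses. Even with equal SDs, at 6 per arm ANCOVA adds 1.5 points at r = 0.7 and has a variance ratio of 1.01 at r = 0.8 (1.125 × 0.90).

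Most of this stands. A reader might infer that the planned test is biased or inflates type I error. It does neither; the higher rates hold only given an imbalance. A reader might also infer that ANCOVA is sure to gain power, and the table shows otherwise.

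The simulations assume equal arms. Simple randomization gives exactly 10/10 with probability 184,756/1,048,576 = 18%. Unequal arms change the power levels but not the ratio, because 1/n1 + 1/n2 multiplies both variances.

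What the objection does not remove is the undefined baseline, which affects the sponsor's own t-test. Nor does it remove the asymmetry at N = 20: gains of up to about 14 points against losses of 2 to 3.

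**Conclusion.** The point holds as a recommended improvement, not as a correction of an error. Its two parts differ in weight.

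The baseline definition is needed under any analysis. A reader might infer that baseline is post-graft. The documents do not say so; they leave it open, and that is the defect.

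ANCOVA is worth prespecifying, most clearly at N = 20. With equal SDs and r from 0.3 to 0.7, the variance ratio is 0.69 to 0.90 at 10 per arm and 0.73 to 0.96 at 6 per arm. With SD12 at 1.5 to 2 times SD0 it is 0.93 to 1.06, or 0.98 to 1.13. The expected variance loss is at most 6.25% (N = 20) or 12.5% (N = 12), which is up to 2 to 3 power points in the cells shown. If the effect is instead set so that the t-test has 80% power, the worst losses are about 3 points at N = 20 and 5 at N = 12.

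All sizes rest on assumed r and SD ratios. That SD12 exceeds SD0 is an inference from the entry criterion, not a documented figure.

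**What to change.** 1. In SAP section 3, state that baseline, for the change score and for any covariate, is GT read before grafting at the protocol's GT site, and that a post-graft reading must not be used as a covariate. Align the timing given in the protocol's assessment methods.
2. In SAP section 6, before any outcome data are seen, name as primary an ANCOVA of 12-month GT on arm and pre-graft GT. Report the adjusted mean difference with 95% CI and two-sided p. Using change as the outcome gives the same treatment estimate. Keep the t-test on change as supporting. Tie the timing to outcome data and not to unblinding, since the SAP blinds only the evaluator.

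**Cost.** Two or three lines of SAP text; SPSS, already named in the SAP, fits the model with UNIANOVA. No new data are needed if GT is already read before grafting; otherwise one extra reading per patient. The model uses one degree of freedom. The conflict between 12 and 20 patients must be reconciled separately; it bears on how much ANCOVA can offer.
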